| CP | Conditional Power |
| CRO | Contract Research Organization |
| CRF | Case report form |
| ECG | Electrocardiogram |
| FDA | Food and Drug Administration |
| GCP | Good Clinical Practice |
| IA | Impulsive Aggression |
| ICF | Informed Consent Form |
| ICH | International Conference on Harmonisation |
| IND | Investigational New Drug Application |
| IV | Intravenous |
| IWRS | Interactive web-based randomization system |
| kg | kilogram |
| mcg | Microgram |
| MedDRA | Medical Dictionary for Regulatory Activities |
| mg | Milligram |
| msec | Millisecond |
| PK | Pharmacokinetic(s) |
| PCH | Percent Change in the frequency of IA behaviors per 7 days |
| PO | Oral |
| PP | Per Protocol |
| PT | Preferred term in MedDRA and WHODD |
| SAE | Serious adverse event |
| SAP | Statistical analysis plan |
| SM | Study Medication |
| SOC | System Organ Class in MedDRA |
| TEAE | Treatment-emergent adverse event |
| TESAE | Treatment-emergent serious adverse event |
| WHODD | WHO Drug Dictionary |

Summary of Changes to the Version 1.0 SAP Submitted to FDA

| Section | Page | Description of Change | Rationale |
|----------------|-------|--|--|
| Signature Page | | Updated signatory information | Administrative |
| 1 | 9 | 
 a. The protocol version and date are updated b. The CRO name for MCIC determination is updated c. A sentence is added to state that this SAP does not cover the population PK analysis method | Protocol amendment V8.0 Administrative |
| 2.2 | 9 | “Oppositional defiant disorder” is added to the SNAP-IV rating scale | This subscale was omitted in the last version of SAP |
| 3.1 | 10-13 | 
 a. Age range changed from “6-17” to “6-12”. This update and removal of “13-17” are found in multiple sections. This description will not be repeated below b. Treatment schedule diagrams are updated to reflect the change/correction in the study day ranges for the screening and baseline periods c. A brief paragraph is added to the end of the section to describe the planned interim analysis | Protocol amendment V8.0 |
| 3.2 | 11 | A new section titled “Schedule of Visits and Procedures” is added | Administrative |
| 3.5 | 17 | A paragraph is added to describe the changes in the sample size and randomization scheme after the planned interim analysis and the new blinded SD estimate. | Protocol amendment V9.0 Note the effect of sample size increase on the type-I error is controlled by the method of inverse normal p-value combination test (MINP) (Section 6.5.7) |
| 4 | 18 | Added “Baseline Period”, “Titration Period”, “Maintenance Period”, and “Treatment Period” definitions | Clarification |
| 5.1 | 19 | A clarification of the visit range is added for the treatment period | Clarification |
| 5.2 | 20-21 | 
 a. Added “at Visit 6” to clarify caregiver’s timing for CGI-I | Clarification |

| | | | |
|-------|----|---|--|
| | | b. Added “Oppositional defiant disorder” to SNAP-IV ADHD scores c. Protocol Appendix numbers are updated in this section and various sections thereafter. This same description will not be repeated Descriptions for CHQ-PF28 are updated to include reference for the derivation of scores for individual items, multi-item scales, and summaries | Clarification and correction is made to the CHQ-PF28 scoring based on the published manual |
| 5.3 | 22 | Previous Section “5.3 Pharmacokinetic Variables” is removed | PK analysis is not the scope of this SAP |
| 5.4.7 | 23 | Visit range for C-SSRS is corrected | Administrative |
| 5.4.8 | 24 | “by the site coordinator” is added to clarify the subjects who administer the caregivers’s assessment of patient’s IA daily activities | Clarification |
| 5.4.9 | 24 | Inserted sentences describing the ranges of the scale scores | Clarification |
| 6.1 | 25 | Respecified the number of decimal places for some summary statistics in the table presentation | Administrative |
| 6.2 | 26 | Clarified how unscheduled data points will be used in the analysis | Clarification |
| 6.3 | 26 | Updated the reference for the statistical method and added two more covariates for the adjustment of covariates: pooled site and baseline IA adjusted to 7 days | Administrative |
| 6.4 | 28 | Expanded text to include methods of deriving weekly IA frequency in the treatment and maintenance period when subject discontinued the study or date of last dose is missing; Replaced LOCF analysis with MMRM analysis for secondary endpoints | To provide detail of how primary endpoint is calculated when diary and dosing data are incomplete replace LOCF method by MMRM with respect to secondary endpoints |
| 6.8 | 37 | To add section number for where to find the multiplicity adjustment | Clarification |
| 6.9 | 35 | Deleted age subgroup of “13-17” | Protocol amendment |
| 7.1.2 | 37 | Added a sentence “Subjects will be analyzed according to the treatment they were randomized to” to the definition of “ITT Population” | Clarification |

| | | | |
|-----------|-------|--|--|
| 7.1.3 | 38 | a. Changed diary completion compliance requirement from “80%” to “70%” for the per protocol population b. Added words “within the treatment period” in the diary compliance formula | To allow more patients in the PP analysis Clarification |
| 7.2 | 38-39 | a. Corrected a typographic error b. Clarified what populations will be used for the disposition summary | Administrative |
| 7.3 | 39 | Added information for protocol deviation summary | Clarification |
| 7.5 | 39 | Specified analysis population for the baseline summary | Clarification |
| 7.6.1 | 40 | Added word “treatment” to read “treatment compliance” to differentiate from “diary compliance” | Clarification |
| 7.7.2.1 | 42-43 | Expanded the section to provide further details for the imputation procedure | Clarification for missing data imputation |
| 7.7.3 | 44 | Analysis of the maintenance period is added | Administrative |
| 7.7.4 | 44 | Renumbered from previous Section 7.7.2.3 | Administrative |
| 7.7.5 | 44 | a. Renumbered from previous Section 7.7.2.4 b. Added 2 new covariates c. Updated the statistical reference | Administrative |
| 7.7.6 | 44 | Defined CGI-I from caregiver and PI as key secondary efficacy variable | Clarification |
| 7.7.7 | 44-47 | a. Clarifies the visit numbers for the by-visit analysis and change from baseline analysis b. MMRM is added for the CGI-I and CGI-S analysis with detailed specifications and sample SAS code c. Clarified other secondary endpoints will be analyzed by ANCOVA d. Added a paragraph to clarify the multiplicity adjustment for the secondary endpoints | Clarification |
| 7.8 (old) | | Removed Pharmacokinetic Analysis section | out of the scope for this SAP but will be defined in separate document |
| 7.8.1 | 48 | Added a few clarifications for AE summaries | Clarification |

| 7.8.2 | 49 | Added a clarifications for lab summaries | Clarification |
|------------|----|--|----------------|
| Reference | 51 | a. Included HealthActCHQ as the reference for CHQ-PF28 scoring b. Reference for the covariate adjustment is updated from "Zink and Koch, 2012" to "Dmitrienko and Koch, 2017" | Administrative |
| Appendix 2 | 54 | Various tables and listings numbers and titles are updated as a result of the SAP text change | Administrative |

1 INTRODUCTION

The purpose of this statistical analysis plan (SAP) is to ensure the credibility of the study findings by specifying the statistical approaches to the analysis of the data prior to database lock. This SAP covers the planned analyses of all data collected on the eCRFs and diary pages, and will identify handling of data issues. The statistical analysis plan presented in this document will supersede the statistical analysis methods described in the clinical protocol. Any deviations/changes from the planned analyses described in this SAP will be identified, with justification, in the appropriate section of the clinical study report. This SAP is based on the clinical study protocol 810P301, version 9.0, dated 01 November 2018 and its associated electronic case report forms (eCRF).

This SAP does not cover the analytic methods for the determination of Minimal Clinically Important Change (MCIC) in clinical efficacy. The assessment of MCIC will be performed by [REDACTED], which is a designated CRO to perform this analysis. This SAP also does not cover the methods for the population pharmacokinetic modeling and analysis.

2 STUDY OBJECTIVES

2.1 *Primary Objective*

The primary objective is to assess the efficacy and safety of SPN-810 in reducing the frequency of IA behaviors in pediatric patients with ADHD when taken in conjunction with standard ADHD treatment.

2.2 *Secondary Objectives*

The secondary objectives of the study are to assess the following:

- The effect of SPN-810 on the Clinical Global Impression – Improvement Scale (CGI-I)
- The effect of SPN-810 on the Clinical Global Impression – Severity Scale (CGI-S)
- The effect of SPN-810 on the child's overall health as measured by the Child Health Questionnaire Parent Form 28-item (CHQ-PF28)
- The effect of treating the child with SPN-810 on the parent-child relationship as measured by the Parenting Stress Index – Short Form version 4 (PSI-4-SF)
- The effect of SPN-810 on the caregiver-completed CGI-I
- The effect of SPN-810 on inattention, hyperactivity-impulsivity and oppositional defiant disorder measured by the SNAP-IV Rating Scale

2.3 *Tertiary Objectives*

3 STUDY DESIGN

3.1 *General Description*

Protocol 810P301 is a randomized, placebo-controlled, double blind, multicenter, parallel group, fixed dose study to demonstrate the efficacy, safety, and tolerability of SPN-810 in the treatment of IA in patients aged 6-12 years with ADHD in conjunction with standard ADHD treatment. The study design is presented schematically in Figure 1 and Figure 2. The study is divided into three phases: Pre-Treatment, Treatment, and Conversion/Taper.

Figure 1: Treatment Schedule (Conversion)

[figure not shown]
[figure not shown]

Figure 2: Treatment Schedule (Taper)

Following screening, eligible subjects will enter a flexible 15-day baseline period, at which time the IA diary will be issued to the subject's primary caregiver. At the end of the baseline period, eligible subjects whose primary caregiver has maintained at least 80% compliance with the IA diary will be randomized 1:1:1 to █ mg/day SPN-810, █ mg/day SPN-810, or placebo treatment group. A dose titration schedule will be followed, with dosing in the active treatment groups initiated at █ mg/day and increased approximately every █ days until the target dose is reached. After completing the two-week titration period and the three-week maintenance period, subjects will enter the conversion or tapering phase prior to discontinuing Study Medication (SM), at which time subjects will have the option to enter an open label extension study. This extension study will be conducted under a separate protocol. Subjects who choose to participate in the open label extension will enter that study at a dose of █ mg/day SPN-810.

An interim analysis is planned when approximately 50% of patients have completed or discontinued the study. This interim analysis is conducted by an independent unblinded statistician for Stage 2 sample size adjustment, if necessary.

3.2 Schedule of Visits and Procedures

All subjects who are randomized and take any study medication (SM) will be followed according to the protocol regardless of the number of doses of SM taken, unless consent for follow-up is withdrawn. Table 1 below presents the schedule of visits and procedures for the study.

Table 1: Schedule of Visits and Procedures

| Phase | Pre-treatment | | Treatment | | | | Conversion/ Taper |
|--|-----------------------|-----------------------|------------------|--------------------|---------------------|---------------------|----------------------|
| | Screening | Baseline | Titration | | Maintenance | | |
| VISIT NUMBER | 1 | 2 | 3 | 4 | 5 | 6 | 7 |
| DAY | -45 | -15 | 1 | 8 | 15 | 36 | 43 |
| WINDOW (DAYS) | ≤45d prior to Visit 3 | ≤15d prior to Visit 3 | 0 ^c | 7d±2d from Visit 3 | 14d±2d from Visit 3 | 21d±3d from Visit 5 | 7d±1d from Visit 6 |
| Informed Consent/Assent ^a | X ^b | | | | | | |
| R-MOAS, K-SADS-PL 2013 & Vitiello Aggression Scale | X | | | | | | |
| Medical History | X | | X ^d | | | | |
| Demographics | X | | | | | | |
| Physical Examination | X | | | | | | X |
| ECG (12-lead) | X | | | X | | | X |
| Inclusion/Exclusion Criteria | X | | | | | | |
| Randomization | | | X ^{b,e} | | | | |
| Urine Drug Screen | X | | X | | | | |
| Urine Pregnancy Test ^f | X | | X | | | | X |
| Diary Training & Distribution or Evaluation | | X | X ^e | X | X | | X |
| Vital Signs ^g | X | | | | | | X |
| Weight, height, BMI | X | | X | X | X | | X |
| Hematology/chemistry/Urinalysis | X | | X | | | | X |
| PK Blood Sampling | | | | X ^h | X ^h | | |
| Columbia Suicide Severity Rating Scale (CSSRS) | X | | X | X | X | | X |
| Investigator CGI-S | X | | X | X | X | | X |
| Caregiver and investigator CGI-I | | | | X | X | | X |
| Efficacy scales (SNAP-IV, CHQ-PF28, PSI-4-SF) | | | X | | | | X |
| Safety Scales (Simpson-Angus, Barnes, AIMS) | | | X | X | X | | X |
| Infrequent Behaviors Checklist | | | X | X | X | | X |
| Adverse Events | | | X | X | X | | X |
| Concomitant Medications | X | X | X | X | X | | X |
| Drug Dispensation | | | X ^b | | X | | |

| Phase | Pre-treatment | | Treatment | | | | Conversion/ Taper |
|----------------------------|-----------------------|-----------------------|----------------|--------------------|---------------------|---------------------|----------------------|
| Period | Screening | Baseline | Titration | | Maintenance | | |
| VISIT NUMBER | 1 | 2 | 3 | 4 | 5 | 6 | 7 |
| DAY | -45 | -15 | 1 | 8 | 15 | 36 | 43 |
| WINDOW (DAYS) | ≤45d prior to Visit 3 | ≤15d prior to Visit 3 | 0 ^c | 7d±2d from Visit 3 | 14d±2d from Visit 3 | 21d±3d from Visit 5 | 7d±1d from Visit 6 |
| Drug Return and Compliance | | | | | X | X | X |
| Diary Return | | | | | | | X |

a Written consent must be obtained prior to performing any study-related procedure.

b Access IWRS.

c Visit 3 will occur at least 15 days following Visit 2

d Assess for any clinically significant change in Medical History since screening.

e Diary compliance must be at least 80% (minimum of 12 days out of 15) to qualify for randomization.

f To be performed for female subjects of childbearing potential prior to administration of first dose of SM and will have to be tested as negative for the subject to continue in the study.

g Heart Rate (HR), blood pressure (BP), temperature, and respiratory rate will be measured.

h Total of 5 PK blood samples will be obtained over one or two visits (Visit 4 and/or Visit 5)

3.3 Study Treatment

3.3.1 Treatment, Dose, and Mode of Administration

SPN-810 (molindone hydrochloride extended-release tablet) or matching placebo tablets will be administered orally (PO) twice daily (BID). Subjects will be force-titrated over a period of 2 weeks to their final randomized dose.

- Treatment 1: placebo
- Treatment 2: [REDACTED] mg total daily dose (TDD)
- Treatment 3: [REDACTED] mg TDD

3.3.2 Duration of Treatment and Study Duration

Total subject duration on study is approximately 13 weeks.

- Pre-treatment phase: 45 days
 - Screening period: up to 30 days
 - Baseline period: at least 15 days
- Treatment phase: 5 weeks
 - Titration period: 2 weeks
 - Maintenance period: 3 weeks
- Conversion/Tapering phase: 1 week

3.3.3 Methods of Assigning Subjects to Treatment Group

Allocation of study drug will be completed centrally through the use of an interactive web response system (IWRS) that will determine which kit to assign to the subject. Separate schedules for subject randomization and drug list will be created. The randomization scheme assigns treatment to each randomization number in a 1:1:1 allocation ratio.

Upon admission to the study, subjects will be assigned site ([REDACTED]) numbers and subject numbers [REDACTED], in the sequence that they are entered. Subjects who complete the Baseline Period and continue to meet all eligibility criteria will be assigned kit numbers, according to the randomization schedule, by using the IWRS.

3.3.4 Blinding

Subjects, all site personnel, the Sponsor and its designated Contract Research Organizations (CROs) are blinded with the following exceptions. The CRO and Sponsor personnel who are

involved in the randomization generation, study drug supply, and PK concentration assays are unblinded. However, they are not involved in the routine study monitoring, data cleaning and review, the design of this SAP or data analysis.

3.4 *Hypotheses*

The null and alternative hypotheses are:

- H_{01} : There is no difference between SPN-810 █ mg and Placebo in the treatment of IA in subjects with ADHD in conjunction with standard ADHD treatment.
- H_{a1} : There is a difference between SPN-810 █ mg and Placebo in the treatment of IA in subjects with ADHD in conjunction with standard ADHD treatment.
- H_{02} : There is no difference between SPN-810 █ mg and Placebo in the treatment of IA in subjects with ADHD in conjunction with standard ADHD treatment.
- H_{a2} : There is a difference between SPN-810 █ mg and Placebo in the treatment of IA in subjects with ADHD in conjunction with standard ADHD treatment.

3.5 *Determination of Sample Size*

Based on results from the Phase 2 study, it is assumed that the average treatment difference between SPN-810 dose groups and placebo is 15 with a common standard deviation of 27.3 in the primary efficacy endpoint. A sample size of 77 subjects per arm (231 subjects for 3 arms) will yield 90% power to detect a non-zero difference between the median of active drug group █ mg or █ mg dose) and the placebo group using the Wilcoxon rank-sum test with a 2-sided significance level $\alpha=0.05$.

It is assumed that approximately 20% subjects will dropout before the completion of the study and hence, an adjusted total of 291 subjects will be randomized in a 1:1:1 ratio to obtain 231 subjects in the ITT population at the completion of the study.

To estimate the variability for designing Study 810P503, the standard deviation (SD) of the primary endpoint for Study 810P301 was reviewed blindly. This review indicates that the SD for interim data was actually 34.83 instead of the protocol-assumed 27.3 (see above). This increase in the SD resulted in the increase in the sample size to 122 subjects per treatment. Allowing for 20% dropout, the final sample size for randomization is 153 subjects per treatment.

The sample size was calculated using the nQuery Advisor Software, Version 7.

3.6 *Changes to Analyses Planned in the Protocol*

This SAP will be updated as necessary if any changes in the protocol occur due to the expected protocol amendment impacting the SAP.

4 DEFINITIONS AND DERIVED DATASETS

Table 1. Terminology and Definition

| Terminology | Definition |
|-------------------------|---|
| Study Medication | SPN-810 or the matching placebo. |
| Study Day | The first dose date (Day 1) is defined as the date on which a subject took the first dose of double-blind study medication (SM), Other study days are defined relative to the Study Day 1. For visits prior to the first dose of the SM, Study Day is calculated as Visit Date – Day 1. For visits after the first dose, Study Day is calculated as Visit Date – Day 1 +1. |
| Enrolled | Subject has provided signed informed consent. |
| Randomized | Subject is assigned with the kit number for the SM. |
| Completer for the Study | Subject who completes the maintenance period (Visit 6). |
| Baseline | Unless specified otherwise, baseline is defined as the non-missing value collected most recent to and before the time of the very first dose of the SM. |
| Baseline Period | For subject daily IA diaries, on and prior to Visit 3 (inclusive, ≤Day 1). |
| Prior Medication | Medication collected on the Prior/Concomitant Medication CRF, with the start date prior to Study Day 1. |
| Concomitant Medication | Medication collected on the Prior/Concomitant Medication CRF, with end date on/after Study Day 1. |
| Titration Period | For subject daily IA diaries from Visit 3 through Visit 5 (v3< to ≤ V5) |
| Maintenance Period | For subject daily IA diaries from Visit 5 through Visit 6 (V5< to ≤ V6) |
| Treatment Period | Titration and Maintenance Periods combined |
| Derived Dataset | Derived dataset (analysis dataset) is any permanently stored collection of data containing raw and/or derived variables created to support the production of statistical summary tables. Derived variables will be created from the “raw” data. Analysis datasets to be created will include ADEFF (efficacy analysis dataset), ADSL (subject-level analysis dataset), ADAE (Adverse event analysis dataset) and other as appropriate. In deriving ADEFF, the source data include both the episodic diary and evening diary data files. Specifications for derived datasets will be developed which will include the names and definitions of derived variables in the derived SAS datasets. |

5 EFFICACY AND SAFETY VARIABLES

5.1 Primary Efficacy Variable

The primary efficacy endpoint is percent change (PCH_T) in the frequency (unweighted score) of IA behaviors per 7 days in the treatment (titration and maintenance) period relative to the Baseline period calculated over the number of days with non-missing IA diary data.

PCH_T will be calculated as $100 \times (T - B)/B$, where T and B are IA behavior frequencies per 7 days during the treatment period (from Day 2 through Visit 6, inclusive) and baseline period (Day ≤ 1), respectively. The IA behavior frequency per 7 days is defined as $(SUM/DAY) \times 7$, where SUM is the total of the IA behaviors reported in the subject IA diary, and DAY is the number of days with non-missing IA score in the subject IA diary during the specified study period.

This primary efficacy variable will be based on a checklist of 15 IA behaviors collected in an electronic IA diary. The IA diary comprises two parts: 1) An episodic diary that will be used by the primary caregiver (or alternate) to enter events as soon as possible after they are observed; and 2) an evening diary that will prompt the caregiver to review events for the day and to enter any events that were not previously captured. Each event will be characterized by a checklist of 15 observed behaviors: Yelling, Screaming, Threatening, Scratching, Throwing, Slamming, Hitting Self, Arguing, Cursing, Name Calling, Shoving, Hair Pulling, Fighting, Hitting Others, and Kicking Others. The checklist will indicate whether each behavior was observed (coded 1) or was not observed (coded 0) during the incidence of an event. Each day can have multiple events. A day can have no event, as can be attested in the evening diary. In this case, if no event is reported during a day, and the evening diary confirms this, the daily event score for that subject will be 0 for each of the 15 IA variables. Behaviors not on this list will not be captured.

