4.3 Treatments

4.3.1 Treatments Administered

Subjects will take molindone hydrochloride extended-release tablet (SPN-810) or placebo twice each day (BID) with or without food, in the morning and in the evening, in addition to the stable dose of the optimized ADHD medication determined from the lead-in period. If initiating treatment before noon, patients should start with the morning dose; if after noon, the evening dose.

Subjects will be randomized to one of three treatments at Visit 3. Subjects will be titrated up to the final randomized total daily dose (TDD).

- Reference treatment
 - Treatment 1: Placebo tablets, PO, BID
- Test treatments
 - Treatment 2: Molindone extended-release tablets, 18 mg TDD, PO, BID
 - Treatment 3: Molindone extended-release tablets, 36 mg TDD, PO, BID

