4.3.6 Dosing Schedule

During Visit 3, subjects will be randomized to Treatments 1, 2, or 3 and start dosing. [Table 2](#) below presents the details of the dosing schedule for each active treatment group throughout the 6-week treatment phase for this study. Dose reduction will not be permitted in the study.

Table 2: Dosing Schedule (Total Daily Dose)

Treatment Arm	Final Dose	Study Days					
		1-2	3-5	6-8	9-11	12-14	15+
Period*		T	T	T	T	T	M
1	Placebo	PBO	PBO	PBO	PBO	PBO	PBO
2	18 mg	■	■	■	■	■	■
3	36 mg	■	■	■	■	■	■

* T = titration period; M = maintenance period; PBO=Placebo

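### The diary baseline for the primary endpoint includes the first-dose day, which is partly post-dose and which the protocol's dosing table labels as titration

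*SAP*

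**What the plan says.** The endpoint is PCH_T = 100 × (T − B)/B. SAP 5.1 measures T and B "during the treatment period (from Day 2 through Visit 6, inclusive) and baseline period (Day ≤ 1), respectively". The passages that bear on the boundary day are:

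- SAP 4, meaning of Day 1: "The first dose date (Day 1) is defined as the date on which a subject took the first dose of double-blind study medication (SM").
- SAP 4, Baseline Period: "For subject daily IA diaries, on and prior to Visit 3 (inclusive, ≤Day 1").
- SAP 4, Titration Period: "For subject daily IA diaries from Visit 3 through Visit 5 (v3< to ≤ V5"). Day 1 is therefore not in T.
- SAP 4, Baseline (general rule): "baseline is defined as the non-missing value collected most recent to and before the time of the very first dose of the SM". This rule yields wherever something else is specified.
- Protocol 4.3.6: "During Visit 3, subjects will be randomized to Treatments 1, 2, or 3 and start dosing". Table 2 in that section marks Study Days 1-2 with T, for titration.
- Protocol 4.3.1: "If initiating treatment before noon, patients should start with the morning dose; if after noon, the evening dose".
- Protocol 6.9.1: the treatment period of the primary endpoint is titration plus maintenance.
- SAP 5.1: the diary ends with an evening review of the whole day, and only days with a non-missing score are counted.
- Protocol 4.2.3, 3.2.1.2 and Table 1: Visit 3 is at least 15 days after Visit 2, the diary may run up to 15 days longer, and at least 12 of 15 days must be complete.

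**The concern.** B is meant to describe the child before treatment. As defined, it contains the day on which treatment starts. A subject who doses in the morning can spend most of that diary day on study drug. The number of post-dose hours counted in B then depends on the clock time of the visit.

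The two documents also assign the day differently. On the protocol's labels Day 1 is titration, which belongs to the treatment period. Protocol 3.2.2.1 likewise randomizes at Visit 3 (Day 1) subjects who have already completed the baseline period. The SAP counts the day as baseline and gives no reason.

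At stake is a small dilution. If behaviors fall on Day 1 because of drug, B is too low and the recorded improvement is too small.

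**Working it through.** **Scale check.** SAP 3.5 gives a difference of 15, SD 27.3, two-sided α = 0.05, 90% power and 77 per arm. With Noether's formula for the Wilcoxon test, n = (z₀.₉₇₅ + z₀.₉₀)² / [6(p − 0.5)²] and p = Φ(15/(27.3√2)). This gives n = 76.6, so 77 is reproduced. The same formula gives 90.1% power at n = 77.

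**Weight of Day 1 in B.** With k non-missing pre-dose diary days the weight is 1/(k + 1):
- k = 12 (minimum compliance): 1/13 = 7.7%
- k = 15 (minimum schedule, all days complete): 1/16 = 6.3%
- k = 30 (longest baseline, all days complete): 1/31 = 3.2%

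**Effect on the endpoint.** Let the true pre-dose frequency be 1, the true proportional change c, and f the share of c already present on Day 1. Then B = (k + 1 + f·c)/(k + 1), T = 1 + c, and the recorded change is 100(T − B)/B. The documents give no arm-level changes. I assume c = −0.40 on active and −0.25 on placebo, which gives the SAP's difference of 15.

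Worked case, k = 15 and f = 1 in both arms:
- Active: B = 15.60/16 = 0.9750, recorded change 100(0.60/0.9750 − 1) = −38.46.
- Placebo: B = 15.75/16 = 0.9844, recorded change 100(0.75/0.9844 − 1) = −23.81.
- Difference: 14.65, a loss of 0.35.

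Recorded difference (true value 15.00), same f in both arms:

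| k | f = 0.25 | f = 0.5 | f = 1 |
|---|---|---|---|
| 12 | 14.90 | 14.79 | 14.57 |
| 15 | 14.92 | 14.83 | 14.65 |
| 30 | 14.96 | 14.91 | 14.83 |

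Recorded difference if only active subjects change on Day 1:

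| k | f = 0.25 | f = 0.5 | f = 1 |
|---|---|---|---|
| 12 | 14.53 | 14.06 | 13.10 |
| 15 | 14.62 | 14.24 | 13.46 |
| 30 | 14.81 | 14.61 | 14.22 |

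At n = 77 and k = 15, the active-only row corresponds to power of about 89%, 87% and 83%. The results are nearly the same at the SAP's later figures of 122 per arm and SD 34.83 (88.5%, 86.8% and 83.0%). If the protocol's difference of 11.51 replaces 15 (assumed changes −36.51 and −25), the shared-effect case at k = 15 gives 11.37 for f = 0.5 and 11.22 for f = 1.

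**Type I error.** If the drug does nothing, Day 1 is handled identically in arms with the same distribution, so the rank test keeps its size.

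**A wording gap at the same boundary.** In SAP 4, baseline ends at Visit 3 and at Day 1, as if these were always one date. If a first dose were taken later, the days from just after Visit 3 up to first dose would be titration by the Visit 3 rule and baseline by the Day ≤ 1 rule. The SAP does not say which governs.

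**The case against.** The inclusion is stated twice and fits the SAP's start of treatment after Visit 3. A whole-day diary cannot be split at the dose time, so the mixed day must go to baseline, to treatment or to neither. Putting it in baseline is conservative. All of that stands.

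A reader might infer three stronger things that the documents do not support:

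- **That a full post-dose day enters every subject's denominator.** The Day 1 score also covers the hours before Visit 3 and dosing. Subjects who start after noon take only the evening dose, so most of their Day 1 is pre-dose. A missing Day 1 score is not counted at all.
- **That the SAP breaks its own baseline rule.** The general rule allows exceptions, and the diary baseline is one.
- **That the endpoint is materially biased or power is seriously reduced.** The 83% figure needs the whole treatment effect on the first day, on active only. Protocol 3.2 starts active dosing at 3 mg/day, so an effect near the low end is more likely. An expectation effect in blinded families would arise in both arms and largely cancel.

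It can also be said that at the minimum schedule the first of the 15 pre-dose days is Visit 2 itself, when the device is issued, which leaves 14 complete days after it. That is fair, and still ample.

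The claim that the protocol sets no competing boundary does not stand, because Table 2 labels Day 1 as titration.

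**Conclusion.** The point holds as a minor defect in the definition of the confirmatory endpoint. The first-dose day, which is partly post-dose, sits in B for every subject with a Day 1 score, and the protocol's dosing table assigns that day to titration.

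The likely cost is about 0.1 to 0.4 points of a 15-point difference, always toward zero if Day 1 behaviors fall because of drug. With a 30-day baseline it is 0.04 to 0.17 points in the shared-effect case. The active-only, full-effect result (a loss of 1.54 points at k = 15) is an upper bound and not an expectation. These sizes rest on the assumed −40% and −25% changes and on f, none of which the documents give. There is no inflation of type I error.

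**What to change.** In SAP 4 and 5.1, define the diary baseline as the days before the first-dose date (Day ≤ −1) and keep treatment from Day 2, so that Day 1 is in neither period. Tie both limits to the first-dose date, which also closes the Visit 3 gap. Derive bwk in the imputation models (SAP 7.7.2) the same way. At least 15 pre-dose diary days are already scheduled, so no data collection changes.

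Stage 1 and Stage 2 p-values are combined in the final test (SAP 6.5.7), so one definition must serve both. The SAP's summary of changes describes sample size changes after the planned interim analysis, which suggests that Stage 1 has already been analyzed. If Stage 1 is fixed on the current definition, keep that as primary, prespecify the Day ≤ −1 version as a sensitivity analysis, and record the difference from protocol Table 2 in SAP 3.6.

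The cost is a re-derivation of Stage 1 or one extra table. The MCIC scores are outside this SAP (SAP 1) and would need the matching change in their own plan.
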